5 STUDY POPULATION

5.1 INCLUSION CRITERIA

- Diagnosis of aMCI: in general, the diagnosis of aMCI follows the definition in the 2011 National Institute on Aging (NIA)/ Alzheimer's association (AA) guidelines, without biomarkers.¹³³ Participants must have:
 - Subjective memory concerns reported by the participant, study partner, or clinician.
 - A mini-mental state exam ≥ 22 for participants with more than 8 years of education. For participants with less than 8 years of education, a MMSE ≥ 20 will be allowed.
 - Clinical Dementia Rating (CDR) = 0.5. The memory box score must be at least 0.5. Information from the formal University of Washington CDR instrument, report by the participant of subjective cognitive complaints, and findings from the screening neuropsychological battery, can be used for this determination by the investigative team. For example, the University of Washington CDR can be 0, but the CDR memory box score can be deemed to be 0.5 based on cognitive complaints at screening and meeting the MCI neuropsychological criteria.
 - General cognition and functional performance sufficiently preserved such that a diagnosis of dementia cannot be made by the site physician at the time of the screening visit.

- Abnormal memory function documented by scoring within the education adjusted ranges on the Logical Memory II subscale (Delayed Paragraph Recall, Paragraph A only) from the Wechsler Memory Scale-Revised.
 - For early MCI:
 - 9-11 for 16 or more years of education
 - 5-9 for 8-15 years of education
 - 3-6 for 0-7 years of education
 - For late MCI:
 - ≤ 8 for 16 or more years of education
 - ≤ 4 for 8-15 years of education
 - ≤ 2 for 0-7 years of education
- Age range: 55 years to 90 years.
- Sex distribution: all eligible men and women will be included, and no one will be excluded because of gender.
- Languages: fluent in English or Spanish. We have reliable, well-validated Spanish tests for all outcome measures.
- Participants without a known history of diabetes. If diabetes is diagnosed during screening (hemoglobin A1c [HbA1c] of 6.5% or greater) participants will be excluded. The main justification for this exclusion is the potential for these participants to be placed on other diabetes medications that may confound our study.
- General cognition and functional performance such that a diagnosis of dementia cannot be made at the time of screening based on DSM-V criteria.

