metformin. Vital signs including blood pressure and heart rate will be measured. Standing height will be measured using a stadiometer calibrated in cm. Body weight is measured using a balance beam scale calibrated in kg. With the participant standing, measurements are taken to the nearest 0.1 kg of weight with a balance scale and height without shoes to nearest 0.5 cm, to calculate BMI (weight in k/height in m²). Waist circumference (WC) is measured at the level of the umbilicus. Hip circumference (HP) is measured at the level of maximal protrusion of the gluteal muscles. Resting blood pressure (BP) will be measured using an automated oscillometric device; three measurements will be obtained at 1-minute intervals in a seated position after 5 minutes of rest. The average of the 2nd and 3rd measurements will be recorded. Vital signs and anthropometric measures will be repeated at all visits. A full physical exam will be repeated at follow-up visits only in the case of a change in medical history.

Neuropsychological battery

The following battery will be administered at baseline and 6-month visits. For neuropsychological testing, verbatim instructions for administration and specific scoring guidelines will be available. All instruments in the neuropsychological battery are commonly used, validated, published instruments. Non-verified or unpublished instruments are not used in this research study. All tests are validated in English and Spanish. We will use different versions of the tests when available (e.g., different word lists) to account for learning effects. The following is an expanded description of the neuropsychological battery:

- Total Recall Score of the Free and Cued Selective Reminding Test (FCSRT). The FCSRT is a 16-item word list with visual and auditory presentation that uses semantic cuing to facilitate encoding and retrieval. The test has a score range of 0 to 48.
- Paragraph Recall on the Logical Memory Ila (episodic memory): Free recall of one short story that consists of 25 bits of information will be elicited immediately after it is read aloud to the participant and again after approximately 30-minute delay. The total bits of information from the story that are recalled immediately (maximum score = 25) and after the delay interval (maximum score = 25) are recorded. The delay score (0-25 story units) will be used in the composite and also for the inclusion criteria.

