8.2 SAFETY AND OTHER ASSESSMENTS

General questionnaires. We will collect demographic data including date of birth, sex, education, ethnic and racial group, and country of origin.¹⁴⁴ We will measure depressive symptoms with the Geriatric Depression Scale¹⁴⁵. Medical history (e.g., diabetes) and medications will be collected with questionnaires we currently use for other studies.

COVID-19 questionnaire. The questionnaire includes questions about history of COVID-19, positive testing for coronavirus, symptoms and sequelae including memory problems, reinfection, and vaccination. A history of COVID-19 will be examined as a covariate and modifier.

Laboratory tests. All laboratory tests will be conducted under fasting conditions. Screening (BMP, HbA1c, lipids, hepatic profile, CBC, RPR, B12 levels, TSH) will be conducted at the central laboratory at the Center for Advanced Laboratory Medicine (CALM) at Columbia. BMP, HbA1c, hepatic profile, lipids, B12 levels, and CBC will be repeated at each visit for safety purposes. TSH and RPR will not be repeated at the follow-up visits. APOE will be genotyped (ϵ 2, ϵ 3, and ϵ 4 alleles) by LGC genomics (Beverly, MA; <http://www.lgcgroup.com>) using single nucleotide polymorphisms (SNPs) rs429358 and rs7412. APOE- ϵ 4 will be examined as a covariate and potential modifier. At the end of the study, we will conduct the following laboratory tests in stored samples to examine the impact of the intervention on intermediate outcomes: Insulin levels will be measured using a solid-phase chemiluminescent enzyme immunoassay (Immulite, Diagnostic Products Co, Los Angeles, CA). Inflammatory markers will include hsCRP, serum Amyloid A, IL-6, IL-8, IL-1B, TNFa, WBC, MCP-1 will be measured using ELISA (Diagnostic Systems Laboratories, Inc., Webster, Texas). We will use the American Diabetes Association criteria for HbA1c to diagnose diabetes (HbA1c 6.5% or greater).¹⁴⁶ We will calculate the homeostatic model assessment (HOMA)¹⁴⁷ using glucose (from the BMP) and insulin values as a measure of insulin resistance.

Adverse events. Gastrointestinal symptoms and development of contraindications to metformin will be queried. Reported symptoms will be further evaluated for severity and duration until they resolve. SAEs will be collected and reported on SAE CRF pages.

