9.4 STATISTICAL ANALYSES

9.4.1 GENERAL APPROACH

Exploratory data analysis will be performed on the entire study sample. All variables will be checked for outlying and unusual observations to detect general patterns, identify gaps and inconsistencies in the data. Visual inspection will be performed by means of box plots, scatterplots, quantile plots and others. Outliers will be checked for possible data entry errors. Reported descriptive statistics for continuous variables will include the number of participants with non-missing observations, median, mean, SD, interquartile range and range, while statistics for categorical variables will include the frequency and percentage of participants in each category.

Adjustment for covariates. In the primary analysis, all models described below will be adjusted for, ApoE- ϵ 4 (as a binary indicator), age (continuous), self-reported sex (male or female) (categorical), baseline total recall FC-SRT score (continuous), MMSE score (continuous), BMI (continuous) and HbA1c level. Additional adjustment for site, BMI, gender, race, educational attainment, COVID-19 history, and white matter hyperintensity will be done as sensitivity analyses. Statistical tests will be two-sided.

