9.4.2 ANALYSIS OF THE PRIMARY EFFICACY ENDPOINT(S)

Analytic Plan for the Primary Aim. The primary aim for this study is to compare changes from baseline to 18 months in verbal memory performance, measured with total recall in the FC-SRT, between the metformin and placebo arms. The primary null hypothesis H0 states that there is no difference between metformin and placebo arms on change in total recall in the FC-SRT from baseline to 18 months of follow-up. We will follow the ITT principle in which all randomized participants are analyzed based on the group to which they are randomized regardless of early termination or errors in randomization detected post hoc.

To estimate the average treatment effect, we will use the targeted maximum likelihood estimator (TMLE) of van der Laan and Gruber (2012). This estimator involves adjustment for baseline (i.e., pre-randomization) variables that are correlated with the outcome to improve precision in estimating the average treatment effect for FC-SRT score at 18 months. The estimator also involves adjustment aimed at reducing bias due to informative censoring, that is, participant dropout that may be correlated with the primary outcome. This adjustment for missing outcomes is done through a combination of inverse probability of censoring weights and outcome prediction models. Specifically, the weights and prediction models use the pre-specified baseline variables, study arm, and the post-randomization outcomes at 0, 6, 12, and 18 months. The motivation of this approach is that if the FC-SRT score at a given visit is correlated with the FC-SRT value at the next visit and also with dropout, then adjusting for observed differences in FC-SRT scores for those who dropout versus those who stay on study may reduce bias (under the assumption that censoring is missing at random). This adjustment is implemented by fitting models for dropout as a binary outcome using logistic regression models for the primary outcome based on FC-SRT measured at the previous visit, study arm, and baseline variables.

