As the final step, average FC-SRT score under hypothetical assignment to the active treatment is estimated for each participant at 18 months (regardless of their actual assignment), given their baseline covariates. Similarly, average FC-SRT score under hypothetical assignment to the comparison arm is estimated. The primary analysis estimator of the average treatment effect as a mean difference is defined as the difference between the former and the latter. This analysis will be performed in a software that implements the above estimator: <https://github.com/mrosenblum/RandomizedTrialEnhancedPrecisionEstimator>.

To test the null hypothesis that the average treatment effect equals 0, a Wald statistic will be computed that is equal to the estimator of the average treatment effect divided by its estimated standard error. The standard error will be computed by the non-parametric bootstrap (resampling participants with replacement and recomputing the above estimator), and the 92% confidence interval will be computed using the bias corrected (BC) and accelerated (BCa) method.

Prior to computing the average treatment effect, missing baseline variables will be imputed using the median for continuous-valued variables (such as age and MMSE) and mode for categorical variables (such as site, APOE e4 status, gender, and education level). Intermittent missing outcomes at each time point will be imputed with fitted values from a regression model using all baseline covariates, previous outcomes, and treatment assignment as covariates.

Subpopulation defined by APOE- ϵ 4 genotype. The primary pre-specified subpopulation analysis is in terms of the APOE- ϵ 4 genotype. Two subpopulations will be defined based on the genotype: 1) any APOE- ϵ 4 allele present, i.e. APOE- ϵ 4 positive and 2) no APOE- ϵ 4 allele present, i.e., APOE- ϵ 4 negative). For each of the two subgroups, the above-described estimator will be computed, and the null hypothesis of no difference will be tested at 0.01 level of significance. If any of the three (one for combined population, and one for each of the two subpopulations) primary null hypotheses are rejected at their respective significance levels, the decision will be made to proceed to a phase III trial. COVID-19 history will be explored as a potential modifier of the intervention.

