9.4.7 SUB-GROUP ANALYSES

Analyses of primary and secondary outcomes will be stratified by the following baseline participant characteristics: (primary) APOE e4 status and age, gender, race, site, type of MCI (early vs. late), BMI, cognition and metabolic status, as measured by Hb1Ac.

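### The primary covariate list omits baseline Logical Memory delayed recall and years of education, a missed and probably modest precision gain

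*Protocol*

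**What the plan says.** Protocol section 9.4.1 names the covariates for the primary models: APOE-ε4, age and sex, followed by "baseline total recall FC-SRT score (continuous), MMSE score (continuous), BMI (continuous) and HbA1c level". It then assigns a second group to sensitivity analyses: "Additional adjustment for site, BMI, gender, race, educational attainment, COVID-19 history, and white matter hyperintensity will be done as sensitivity analyses". Education is therefore a sensitivity covariate only. Logical Memory and MCI stage are in neither group. Stage enters the analysis only as a subgroup factor in section 9.4.7, as "type of MCI (early vs. late".

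Section 9.4.2 states what the adjustment is for: "This estimator involves adjustment for baseline (i.e., pre-randomization) variables that are correlated with the outcome to improve precision". Its rule for missing baseline values, applied before the treatment effect is computed, gives as examples the "mode for categorical variables (such as site, APOE e4 status, gender, and education level".

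Both omitted variables are available at baseline. Section 5.1 requires "Abnormal memory function documented by scoring within the education adjusted ranges on the Logical Memory II subscale". Section 8.1 says of the paragraph recall test: "The delay score (0-25 story units) will be used in the composite and also for the inclusion criteria". Section 8.2 says: "We will collect demographic data including date of birth, sex, education, ethnic and racial group, and country of origin". The pilot enrolled late aMCI only (section 2.2.7.1), whereas MAP takes early and late MCI (section 2.2.7.3).

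**The concern.** The outcome is a memory score at 18 months, in a sample widened on purpose to two stages of memory impairment. A second baseline memory score, and the education level against which it is judged, are natural candidates to predict that outcome. An estimator chosen for precision would ordinarily use them, since they are already in the database. The list keeps BMI and HbA1c but leaves out the pair of variables that defines stage.

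The imputation rule adds an uncertainty. It prepares education for use just before the primary estimate, while section 9.4.1 leaves education out of that estimate. A reader cannot be sure which covariates go in.

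At stake is the precision of the estimate that decides whether to proceed to phase III (sections 9.4.2 and 9.4.10).

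**Working it through.** **1. The two variables jointly define stage.** In section 5.1 a delayed recall of 8 is late MCI with 16 or more years of education but early MCI with 8 to 15 years. A score of 4 is late MCI with 8 to 15 years but early MCI with 0 to 7 years. Neither variable gives the stage alone.

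**2. The plan's own figures.** Section 9.2.2 gives d = 0.3, 278 evaluable participants, about 10% annual loss and 326 randomized. It prints α = 0.2 (80% power) and β = 0.1. Read as two-sided α = 0.10 with 80% power:

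- Normal approximation: n per arm = 2(1.645 + 0.842)²/0.3² = 137.4, rounded up to 138, total 276.
- t-test: 138.06 per arm, rounded up to 139, total **278**.
- Loss over 18 months: 278/0.9^1.5 = 325.6, rounded up to **326**.

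Both figures reproduce, and neither uses any covariate. The printed labels taken literally (α = 0.2, 90% power) would give 292.

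**3. Effect of adding the two variables.** Let R²p be the share of the variance left by the listed covariates that delayed recall and education explain together. The documents do not give it; 2%, 5% and 10% are assumed. The standard error is multiplied by √(1 − R²p), and the equivalent sample size is 278/(1 − R²p).

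| R²p | SE factor | Equivalent N | Gain |
|---|---|---|---|
| 2% | 0.990 | 284 | 6 |
| 5% | 0.975 | 293 | 15 |
| 10% | 0.949 | 309 | 31 |

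**4. Power.** Let R²b be the share of outcome variance that the listed covariates already explain (also assumed). At the two-sided α of 0.08 for the whole population:

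power = Φ(0.3 × √(278/4) / √((1 − R²b)(1 − R²p)) − 1.7507)

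| R²b | No addition | R²p 2% | R²p 5% | R²p 10% |
|---|---|---|---|---|
| 0 | 77.3% | 78.1% | 79.3% | 81.2% |
| 30% | 89.2% | 89.8% | 90.6% | 91.9% |
| 40% | 93.0% | 93.5% | 94.1% | 95.1% |
| 50% | 96.3% | 96.6% | 97.0% | 97.6% |

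The gain runs from 0.3 points (R²b 50%, R²p 2%) to 3.9 points (R²b 0, R²p 10%). The first row is an upper bound: the list already contains the baseline value of the outcome, so R²b will not be zero. With R²b of 30% to 50% the gain is 0.3 to 2.7 points.

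**5. Room in the dropout models.** Section 9.4.2 also uses the baseline variables in logistic models for dropout. Planned loss is 326 − 278 = 48 participants, or 16 in each of three six-month intervals if evenly spread. The estimator is rerun in each APOE subgroup. At the pilot's carrier share (21 of 80, 26.25%), the ε4-positive group has about 278 × 0.2625 = 73 evaluable participants and 48 × 0.2625/3 = 4.2 dropouts per interval.

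**The case against.** The plan already has a fixed list that contains the baseline value of the outcome, a second cognitive score (MMSE), age, sex and APOE. Omitting one more prognostic variable from a randomized comparison biases nothing, and use as an entry criterion does not oblige adjustment. Randomization is stratified by site only (section 6.3), so neither variable is a stratification factor. All of this stands.

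Education is also not ignored: it is in the sensitivity adjustment and is named as a possible covariate for the mixed models in section 9.4.2.1. The entry limits cap delayed recall at 11, 9 or 6 according to education, which narrows its range and makes the 10% scenario look optimistic. HbA1c has some support in the pilot's post hoc table (section 2.2.7.1): SRT gains were larger at HbA1c of 6.0% or below in both arms (12.2 against 6.3 on metformin, 6.6 against 4.0 on placebo). The documents offer no comparable data for education or Logical Memory. These points limit the size of the gain but do not remove the case for using data already in hand.

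A reader might infer that sections 9.4.1 and 9.4.2 prescribe two different primary estimates. The text does not go that far. The passage in 9.4.2 is an imputation rule with an open list of examples, and a rule for missing education is needed for the sensitivity models anyway. It leaves the covariate set unclear, but only 9.4.1 defines that set.

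**Conclusion.** The omission is real and sits poorly with the purpose stated in section 9.4.2. Logical Memory is the clearer half, because it is in no adjustment list at all. The consequence is a missed precision gain, probably modest: about 1% to 5% in the standard error and roughly 0.3 to 4 points of power, with the lower part of that range more likely once baseline FC-SRT and MMSE are credited. These sizes rest on an assumed partial R-squared of 2% to 10%, an assumed 0% to 50% of variance already explained, d = 0.3, 278 evaluable participants and α = 0.08.

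A reader might infer that the trial is underpowered because of this list. The documents do not support that. The sample size calculation takes no credit for covariates, and the 77.3% in the first row of the power table reflects testing at 0.08 when 278 reproduces at 0.10 (where power is 80.4%), not the choice of covariates.

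**What to change.** Before unblinding, add baseline Logical Memory delayed recall (continuous) and years of education to the outcome-regression part of the primary estimator in section 9.4.1. Both are needed, because the stage cut-points depend on education. Keep the dropout models to a shorter, pre-specified list where dropouts are few, above all in the APOE-ε4-positive subgroup. Make the baseline variables named for imputation in section 9.4.2 match that single list, and mark any that serve only the sensitivity models. Education entered as years would fall under the median rule rather than the mode rule.

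The cost is a few lines of text, two more parameters in the outcome model, and slightly more complexity in the bootstrap and the APOE subgroup analyses. No additional data collection is required.

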9.4.2 ANALYSIS OF THE PRIMARY EFFICACY ENDPOINT(S)

Analytic Plan for the Primary Aim. The primary aim for this study is to compare changes from baseline to 18 months in verbal memory performance, measured with total recall in the FC-SRT, between the metformin and placebo arms. The primary null hypothesis H0 states that there is no difference between metformin and placebo arms on change in total recall in the FC-SRT from baseline to 18 months of follow-up. We will follow the ITT principle in which all randomized participants are analyzed based on the group to which they are randomized regardless of early termination or errors in randomization detected post hoc.

To estimate the average treatment effect, we will use the targeted maximum likelihood estimator (TMLE) of van der Laan and Gruber (2012). This estimator involves adjustment for baseline (i.e., pre-randomization) variables that are correlated with the outcome to improve precision in estimating the average treatment effect for FC-SRT score at 18 months. The estimator also involves adjustment aimed at reducing bias due to informative censoring, that is, participant dropout that may be correlated with the primary outcome. This adjustment for missing outcomes is done through a combination of inverse probability of censoring weights and outcome prediction models. Specifically, the weights and prediction models use the pre-specified baseline variables, study arm, and the post-randomization outcomes at 0, 6, 12, and 18 months. The motivation of this approach is that if the FC-SRT score at a given visit is correlated with the FC-SRT value at the next visit and also with dropout, then adjusting for observed differences in FC-SRT scores for those who dropout versus those who stay on study may reduce bias (under the assumption that censoring is missing at random). This adjustment is implemented by fitting models for dropout as a binary outcome using logistic regression models for the primary outcome based on FC-SRT measured at the previous visit, study arm, and baseline variables.

As the final step, average FC-SRT score under hypothetical assignment to the active treatment is estimated for each participant at 18 months (regardless of their actual assignment), given their baseline covariates. Similarly, average FC-SRT score under hypothetical assignment to the comparison arm is estimated. The primary analysis estimator of the average treatment effect as a mean difference is defined as the difference between the former and the latter. This analysis will be performed in a software that implements the above estimator: <https://github.com/mrosenblum/RandomizedTrialEnhancedPrecisionEstimator>.

To test the null hypothesis that the average treatment effect equals 0, a Wald statistic will be computed that is equal to the estimator of the average treatment effect divided by its estimated standard error. The standard error will be computed by the non-parametric bootstrap (resampling participants with replacement and recomputing the above estimator), and the 92% confidence interval will be computed using the bias corrected (BC) and accelerated (BCa) method.

Prior to computing the average treatment effect, missing baseline variables will be imputed using the median for continuous-valued variables (such as age and MMSE) and mode for categorical variables (such as site, APOE e4 status, gender, and education level). Intermittent missing outcomes at each time point will be imputed with fitted values from a regression model using all baseline covariates, previous outcomes, and treatment assignment as covariates.

Subpopulation defined by APOE- ϵ 4 genotype. The primary pre-specified subpopulation analysis is in terms of the APOE- ϵ 4 genotype. Two subpopulations will be defined based on the genotype: 1) any APOE- ϵ 4 allele present, i.e. APOE- ϵ 4 positive and 2) no APOE- ϵ 4 allele present, i.e., APOE- ϵ 4 negative). For each of the two subgroups, the above-described estimator will be computed, and the null hypothesis of no difference will be tested at 0.01 level of significance. If any of the three (one for combined population, and one for each of the two subpopulations) primary null hypotheses are rejected at their respective significance levels, the decision will be made to proceed to a phase III trial. COVID-19 history will be explored as a potential modifier of the intervention.

